13.3 Vital Signs

Descriptive statistics will be presented by dosing regimen at Baseline and each post-Baseline visit for data related to vital signs (systolic blood pressure, diastolic blood pressure, pulse rate, respiratory rate, oral temperature, and weight). Change from Baseline values will also be presented at each post-Baseline visit.

A by-patient listing of all vital sign assessments will be provided.

13.4 Physical Examination

Clinically significant deteriorations in physical examination findings will be reported and summarized as adverse events.

A listing of all physical examination assessments will be provided.

13.5 Electrocardiogram

Descriptive statistics will be presented by dosing regimen at Baseline and each post-Baseline visit for data related to ECG parameters (PR, QT, QTcF, QRS, and RR). Change from Baseline values to each post-Baseline visit will be presented.

Additionally, count and percentage of subjects with a QTcF value < 450 msec at Baseline but > 450 msec, > 480 msec, > 500 msec at any time on treatment will be provided. Count and percentage of subjects with a QTcF value < 450 msec at Baseline but a value > 450 msec, > 480 msec, > 500 msec will also be provided for each post-baseline visit. QTcF increase from baseline > 30 msec and > 60 msec among subjects with a QTcF value < 450 msec at Baseline will be summarized similarly.

A by-patient listing of ECG assessments will be provided, including the Investigator's overall ECG interpretation (normal, abnormal NCS, and abnormal CS).

	STATISTICAL ANALYSIS PLAN, Final v1.0
Protocol Number CP543.2003	Sponsor: Concert Pharmaceuticals, Inc.

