- 11. Fever, inflammation, or systemic signs of illness suggestive of systemic or invasive infection within 2 weeks prior to first dose of study drug.
- 12. Abnormal levels of thyroid stimulating hormone at Screening, defined as <0.9 x the lower limit of normal (LLN) and >1.2 x the upper limit of normal (ULN).
- 13. Screening labs outside the normal range for parameters associated with potential risk for treatment under investigation. This will include but is not limited to:
  - a. Platelets  $\leq 120 \times 10^9 / L \text{ or } \geq 600 \times 10^9 / L$
  - b. Absolute neutrophil count  $\leq 1.5 \times 10^9/L$
  - c. Hemoglobin levels  $\leq 11$  g/dL for females, or hemoglobin levels  $\leq 12$ . 5 g/dL for males
- 14. Screening blood glucose levels of hemoglobin A1c ≥6.5% (48 mmol/mol).
- 15. Abnormal liver function at Screening, defined as ≥1.5 × ULN of serum alanine transaminase, serum aspartate transaminase, serum alkaline phosphatase, or total bilirubin (unless isolated Gilbert's syndrome).
- 16. Abnormal renal function (estimated glomerular filtration rate <60 mL/min/1.73 m^2 using the MDRD equation) at Screening.
- 17. Subject has positive results for hepatitis B surface antigens (HBsAg), antibodies to hepatitis B core antigens (anti-HBc), or hepatitis C virus (HCV) at Screening.
- 18. Vaccination with herpes zoster vaccine or plans to receive a live attenuated vaccine during the study and up to 6 weeks or 5 half-lives (of the study product), whichever is longer, after the last study product administration.
- 19. Positive TB test, or history of incompletely treated or untreated tuberculosis.
  - NOTE: In cases where performance of a QuantiFERON-TB Gold test is not possible, testing with a Tuberculin Skin Test (TST) may be an option after consultation with the Medical Monitor. If the TST is negative, patients can be randomized into the study, assuming they meet all other inclusion and none of the exclusion criteria. If results are equivocal, or there is reason to believe the result is a false positive, a QuantiFERON-TB Gold must be performed before a subject is eligible for randomization.
  - NOTE: Subjects with documented completed treated with latent TB are not excluded.
- 20. History of prolonged QT syndrome or a Screening QTc interval with Fridericia's correction (QTcF) > 450 msec for males or QTcF > 470 msec for females.
- 21. History of alcohol, medication, or illicit drug abuse within 1 year before the first dose of study drug.

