5.1 Baseline

Unless otherwise specified, Baseline value will be defined as the last non-missing assessment prior to the first dose of study drug (including repeat and unscheduled assessments). If the last non-missing assessment is performed on the same date as the first dose of study drug and time is not available, the assessment will be considered as Baseline, except for adverse events (AEs) and medications starting on the first study treatment dose date which will be considered post-Baseline.

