6.2 Descriptive Statistics and Common Derivations

Continuous endpoints will be summarized using descriptive statistics (i.e., number of subjects with non-missing data, mean, standard deviation [SD], median, minimum and maximum). Categorical endpoints will be presented as frequencies and percentages. Unless otherwise indicated, the percentages will be computed based on the number of patients included in the concerned analysis population.

Summary tables will be presented by dosing regimen and visit, when applicable.

As the SALT score is by nature a measurement of total surface of the scalp without hair, it is important to note that in the context of this SAP, SALT endpoints will follow these definitions:

Absolute change from Baseline = difference in SALT measurements i.e., Baseline SALT score - post-Baseline SALT score

Relative change from Baseline = percent change of the post-Baseline SALT score, where baseline SALT score is the denominator i.e. (absolute change from Baseline / Baseline SALT score) * 100%

For all other endpoints (e.g., patient satisfaction hair coverage, VAS, patient satisfaction hair coverage quality, clinical laboratory, vital signs, etc.), the change and percent change from baseline will be computed as follows:

Change from Baseline = Assessment value at post-Baseline visit X – Baseline value.

Percent change from Baseline = (change from Baseline / Baseline value]) * 100%.

	STATISTICAL ANALYSIS PLAN, Final v1.0
Protocol Number CP543.2003	Sponsor: Concert Pharmaceuticals, Inc.

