13 SAFETY/TOLERABILITY ANALYSIS

All safety/tolerability analyses will be conducted based on the Safety analysis population by dosing regimen. No statistical inferences will be performed on any safety endpoint. All safety endpoints will be listed in by-patient data listings.

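### The QTcF outlier tables leave out eligible patients who start at 450 msec or above, so the >480, >500, +30 and +60 msec counts can miss events

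*SAP*

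**What the plan says.** SAP section 13.5 plans three sets of categorical QTcF summaries:

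- At any time on treatment: "count and percentage of subjects with a QTcF value < 450 msec at Baseline but > 450 msec, > 480 msec, > 500 msec".
- By post-baseline visit (all values in msec): "Count and percentage of subjects with a QTcF value < 450 msec at Baseline but a value > 450 msec, > 480 msec, > 500".
- Increases, summarized in the same way: "QTcF increase from baseline > 30 msec and > 60 msec among subjects with a QTcF value < 450 msec at Baseline".

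All three carry the same baseline limit, with one value for both sexes.

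Exclusion criterion 20 (Protocol synopsis and section 7.2) works on the Screening ECG and differs by sex. It excludes "QTcF) > 450 msec for males or QTcF > 470 msec for females". Men at exactly 450 msec and women from 450 to 470 msec can therefore be enrolled.

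Three other SAP rules matter here. Section 5.1 sets Baseline by this rule: "Baseline value will be defined as the last non-missing assessment prior to the first dose of study drug". Section 13 states the analysis set: "All safety/tolerability analyses will be conducted based on the Safety analysis population by dosing regimen". Section 6.2 gives the default denominator: "the percentages will be computed based on the number of patients included in the concerned analysis population".

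**The concern.** A baseline limit has a clear purpose for the >450 msec category: a patient already above 450 msec cannot newly cross it. That reason does not carry over to the rest. A patient who starts at 460 msec is below 480 and 500 msec and can newly cross either. An increase above 30 or 60 msec already uses the patient's own baseline. In these four categories the limit does nothing except remove the patients with the longest starting QTcF.

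Tolerability shares the primary objective with efficacy, and the QD arm takes 24 mg in one dose where the BID arm takes 12 mg. The outlier table could show 0% above 500 msec, or 0% with a rise above 60 msec, while the Safety population contains such a patient.

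**Working it through.** The plan gives no figure to reproduce here, so the check compares two rules and then illustrates the size.

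**1. Eligibility against the table limit (whole msec)**

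| | Eligible at Screening | Counted in the 13.5 categories | Eligible but not counted |
|---|---|---|---|
| Men | up to 450 | below 450 | 450 |
| Women | up to 470 | below 450 | 450 to 470 |

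Eligibility is judged on the Screening ECG, but Baseline is the last pre-dose value, and an ECG is scheduled on Day 1. A patient whose Day 1 value has drifted above the Screening limit, if dosed, is left out too. A patient who drifts down below 450 msec is counted. The gap is therefore not bounded by the eligibility range.

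**2. Example patients**

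The SAP rule is compared with a rule that uses all patients for increases and, for each threshold, patients at or below that threshold at Baseline.

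| Patient | Baseline | On treatment | Change | SAP 13.5 counts | Counts for >480, >500, +30, +60 without the 450 limit |
|---|---|---|---|---|---|
| Woman | 449 | 510 | 61 | all five | all four |
| Woman | 465 | 505 | 40 | none | >480, >500, +30 |
| Woman | 465 | 530 | 65 | none | all four |
| Man | 450 | 511 | 61 | none | all four |
| Woman | 470 | 481 | 11 | none | >480 |

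The woman at 449 msec and the man at 450 msec have the same rise of 61 msec. One enters every category and the other enters none.

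**3. Consistency within the SAP**

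Section 13.2 defines a treatment-emergent potentially clinically significant laboratory value as one where Baseline does not meet the criterion and a later value does. Applied to QTcF, that gives a separate baseline condition for each threshold. Section 13.5 instead uses the 450 msec condition for all of them.

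**4. How many patients (illustration)**

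The documents give neither the sex split nor the QTcF distribution. Let f be the share of women and q the share of women at 450 msec or above at Baseline, both assumed, with N = 60 from the Protocol.

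- Expected number left out = 60 × f × q
- Chance of at least one = 1 − (1 − f × q)^60

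| f | q | Expected number | Chance of at least one |
|---|---|---|---|
| 0.50 | 0.02 | 60 × 0.01 = 0.6 | 1 − 0.99^60 = 0.45 |
| 0.50 | 0.10 | 60 × 0.05 = 3.0 | 1 − 0.95^60 = 0.95 |
| 0.80 | 0.15 | 60 × 0.12 = 7.2 | 1 − 0.88^60 > 0.99 |

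These are patients left out, not events missed.

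**5. Effect of one missed event**

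With 30 patients in an arm, one event is 1/30 = 3.3%. If that patient started at 450 msec or above, the table shows 0/30 under the section 6.2 default or 0/29 if the denominator is restricted as well. Section 13.5 does not say which applies. Under the default, the patient sits in the denominator but can never enter the numerator.

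**The case against.** The best reply is that nothing is hidden. Section 13.5 also plans descriptive statistics for QTcF and its change from Baseline at every post-baseline visit, with no baseline limit, and section 6.2 includes the minimum and maximum. A woman who reached 505 msec at a scheduled visit would show in that visit's maximum, and a 65 msec rise in the maximum change. Early termination visits are summarized separately, and a by-patient ECG listing carries the investigator's interpretation. The tables state their own restriction, and the Protocol asks only for descriptive change in ECG intervals, so the categories are an addition. The documents describe no QT signal for CTP-543, the limit is the same in both arms, and no inference is planned on safety. Finally, the prevalence is assumed, and a missed event also needs an affected patient to cross a threshold.

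Most of this stands, and it limits the consequence. It does not justify the limit. A maximum shows that at least one patient was extreme; it does not give the number of patients over a threshold, which is what the outlier tables are for. Under section 5.3, a repeat or unscheduled ECG enters the visit summaries only when the scheduled value is missing, so an excursion seen only there could appear in the listing alone. No reason is given for applying the limit to >480, >500, +30 or +60 msec.

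**Conclusion.** The point holds. As written, section 13.5 leaves every patient with a Baseline QTcF of 450 msec or more out of all five categories, at any time and by visit, and no other categorical table covers them. This follows from the two rules alone and rests on no assumption. The number of patients is not known: 0.6 to 3 if half of 60 are women and 2% to 10% of those start at 450 msec or above, and up to about 7 under the widest assumptions tried. Each missed event is worth about 3.3 percentage points in an arm of 30. The change should be made, but it concerns the completeness of the outlier counts; the underlying data are still reported elsewhere.

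**What to change.** Amend SAP section 13.5 for both the any-time and the by-visit tables:

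- Report increases above 30 and above 60 msec for all Safety patients with a Baseline and at least one post-baseline QTcF.
- For >450, >480 and >500 msec, count patients whose Baseline was at or below that same threshold, so that each category is treatment-emergent in its own right.
- State the denominator for each category, and show how many patients were left out of it because their Baseline was already above the threshold.

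The cost is SAP wording and table programming before database lock. The ECG data are already collected, and no visit, assessment or clinical rule changes.

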14 APPENDICES

Appendix 1

Table 1 provides a description of the procedures planned at each visit.

	STATISTICAL ANALYSIS PLAN, Final v1.0
Protocol Number CP543.2003	Sponsor: Concert Pharmaceuticals, Inc.

Table 1: Schedule of Events

	Screening	Randomization ¹ Day 1 ² (Visit 2)	Treatment Period					Safety Follow-Up
Event	Day -28 to Day -1 (Visit 1)		Week 2, 6 (Visit 3, 5)	Week 4, 8 (Visit 4, 6)	Week 12 (Visit 7)	Week 16, 20 (Visit 8, 9)	Week 24 ³ /ET (Visit 10)	Week 28 ⁴ (Visit 11)
Informed consent	X							
Eligibility assessment	X	X						
Demographics	X							
Medical and surgical history	X	X						
Randomization		X						
Physical examination	X	X					X	X
Brief physical examination				X	X	X		
Height	X							
Weight	X	X		X	X	X	X	X
Pregnancy test ⁵	X	X	X	X	X	X	X	X
Tuberculosis test ⁶	X							
Clinical laboratory testing ⁷⁸	X ⁹	X	X	X	X	X	X	X
Lipid assessment ¹⁰		X			X		X	X
HBV and HCV test	X							
12-lead electrocardiogram	X	X			X		X	X
Vital signs	X	X		X	X	X	X	X
Severity of Alopecia Tool (SALT) assessment ¹¹	X	X		X	X	X	X	
Photographs ¹²	X	X			X		X	
Patient Satisfaction Questions	X	X		X^{13}	X		X	
Visual Analog Scale (VAS) for Eyebrows		X			X		X	
Clinical Global Impression of Severity	X	X		X^{13}	X		X	
Clinical Global Impression of Improvement				X ¹³	X		X	
Patient Global Impression of Severity	X	X		X^{13}	X		X	
Patient Global Impression of Improvement				X^{13}	X		X	
Study Product Administration at study site		X	X	X	X	X		
Dispense study drug		X		X	X	X		
Study drug accountability				X	X	X	X	
Adverse events ¹⁴	X	X	X	X	X	X	X	X
Concomitant medications ¹⁴	X	X	X	X	X	X	X	X

	STATISTICAL ANALYSIS PLAN, Final v1.0
Protocol Number CP543.2003	Sponsor: Concert Pharmaceuticals, Inc.

ET=Early termination; HBV= hepatitis B virus; HCV = hepatitis C virus; PPD = purified protein derivative.

- Randomization/Day 1 may occur any time after Screening laboratory results are available and reviewed by the Investigator.
- ² All subsequent visits and week increments should be based on the date of Visit 2. All visit windows are ±3 days for subsequent visits.
- ³ Also serves as the Early Termination Visit for patient withdrawal in this period.
- ⁴ The Safety Follow-Up Visit is intended for those patients who do not roll over into an open-label extension and for patients who have been discontinued from the study and completed the Early Termination Visit (Week 24).
- ⁵ For females of childbearing potential, a serum pregnancy test will be performed at all visits aside from the randomization visit where a urine pregnancy test will be performed.

- 6 If PPD (skin test) is performed, subject will need to return to the clinic 24-48 hours after placement for PPD reading.
- ⁷ Includes hematology and serum chemistry.
- ⁸ When possible, collect pre-dose, except on Visit 11.
- ⁹ Will include thyroid stimulating hormone and hemoglobin A1c at Screening only.
- ¹⁰ Includes total cholesterol, low-density lipoprotein, high-density lipoprotein, and triglycerides.
- ¹¹ Should be performed by the same rater, when possible, for the patient for the duration of the study.
- ¹² For participants who authorize photographs to be taken of their scalp involvement and/or eye and nail involvement.
- ¹³ Will be conducted at Visit 6 (Week 8) only.
- ¹⁴ Collection is ongoing.

	STATISTICAL ANALYSIS PLAN, Final v1.0
Protocol Number CP543.2003	Sponsor: Concert Pharmaceuticals, Inc.

Appendix 2

Output Conventions

TLF will be generated using SAS® and will be displayed on letter size paper with landscape orientation, 1-inch margins, and 9-point Courier New font.

All TLFs will include a header section comprised of the Sponsor's name, the protocol number, the delivery description, the data cut-off date (if applicable), the TLF number, the TLF title, the analysis population, and the page number (Page X of Y). The footer section will include the TLF footnotes, the CRO's name, the date and time of the execution of the program, and the name of the program.

Summary tables and data listings will be summarized by dosing regimen and overall, as appropriate. All data collected per-protocol and all derived variables will be listed.

Mean and median will be displayed to one more decimal place than the original value; SD and CI will be displayed to two more decimal places than the original value; minimum and maximum will keep the same number of decimal places as the original value. If derived parameters are to be summarized, the number of decimals of the derived values is to be chosen on a case-by-case basis, but the rule above applies.

For categorical summary tables, percentages will be reported to one decimal place. Percentages between 0 and 0.1 (both exclusive) will be displayed as "<0.1". Percentages between 99.9 and 100.0 (both exclusive) will be displayed as ">99.9". For each dosing regimen, the denominator for each percentage will be the number of patients within the population, unless otherwise specified.

Listings will be ordered by dose regimen, patient number, parameter (where applicable), date, and visit (where applicable). Imputed dates and imputed missing data will not be presented in the listings.

All statistical deliverables will be produced, validated, and reviewed for accuracy/consistency in accordance with standard operating procedures.

Dates & Times Format

Date and time (if available) will be presented in the format yyyy-mm-dd/hh:mm.

Presentation of Treatment Arms

When applicable, study treatments will be represented as follows in the different outputs:

	STATISTICAL ANALYSIS PLAN, Final v1.0
Protocol Number CP543.2003	Sponsor: Concert Pharmaceuticals, Inc.

Study Treatment Full Names	Study Treatment Output Names
12 mg BID CTP-543	12 mg BID CTP-543
24 mg QD CTP-543	24 mg QD CTP-543

	STATISTICAL ANALYSIS PLAN, Final v1.0
Protocol Number CP543.2003	Sponsor: Concert Pharmaceuticals, Inc.

Appendix 3

Algorithm for Imputation of Start/End Date of Adverse Events and Prior/Concomitant Medications

Event Start Date Imputation

- Imputation of event end date should be done before imputation of event start date.
- Completely missing: Impute to the date of the first dose of study treatment.
- Missing day and month: Impute to January 1st, unless year is the same as year of first dose
 of study treatment. If so, impute to the date of the first dose of study treatment.
- Missing day: Impute to the 1st of the month, unless month and year are the same as month and year of first dose study treatment. If so, impute to the date of the first dose of study treatment.
- If imputed event start date is after event end date (imputed or not), set the event start date to the imputed event end date.

Event End Date Imputation

- Completely Missing: Impute to the date of the last dose of study treatment.
- Missing day and month: Impute to December 31st, unless year is the same as the date of the last dose of study treatment. If so, impute to the date of the last dose of study treatment.
- Missing day: Impute to the last day of the month, unless year and month are the same as
 year and month of the date of the last dose of study treatment. If so, impute to the date of
 the last dose of study treatment.
